#### - MNA score screening at M-1 and M6

The MNA screening score (*Appendix 5*) will make it possible to measure the number of residents for whom the nutritional status is normal, those at risk of malnutrition and those with proven malnutrition. It will be carried out by the department's nurse.

#### **Associated Comorbidities:**

- Number of wounds and pressure sores per month

New pressure ulcers and their severity will be plotted throughout the study.

- Number of falls per month

The number of falls will be plotted throughout the study.

These comorbidities will be extracted from the ennov software by a clinical research IDE.

#### Autonomy:

Power supply autonomy: EBS at M-1 then at M3 and M6.

Eating autonomy will be assessed using the Eating Behaviour Scale (EBS) (Appendix 6).

The completion of this scale will be done jointly by the caregiver and the housekeeper of the ward. It will identify and monitor the resident's autonomy around the meal, depending on whether the resident is independent, dependent or requires verbal or physical stimulation.

#### Physical or psychological autonomy: GIR at M-1 then M6.

The GIR grid (Groupes Iso-Ressources) will make it possible to evaluate the degree of loss of autonomy or the degree of physical or psychological dependence of the residents in the accomplishment of daily acts (Appendix 7).

This grid will be carried out by the unit's health executive, in collaboration with the care team. This evaluation identifies the resident according to a GIR group ranging from 1 to 6.

#### Mealtime behavior: Blandford at M-1 and then at M3 and M6.

The Blandford scale [24] will allow the caregiver to assess and classify eating

disorders (Appendix 8), according to:

- Resistance behaviors
- Dyspraxia and agnosia
- Selective behaviors
- Neuromuscular oral incoordination
- Food dependency

The realization of this scale will be done jointly by the IDE and the nursing assistant of the service.

**Resident satisfaction / pleasure of eating:** EVA at M-1 (on 3 consecutive days) then monthly on " 3 consecutive days until M6. The average of the evaluations over the 3 days will be taken into account.

This evaluation will be performed by the housekeeper or caregiver and will assess the satisfaction and pleasure of eating expressed by the resident (regardless of the randomization arm).

This evaluation will be done through the satisfaction scale presented in figure 1.

#### Figure 1 – Satisfaction scale

Hospitality/care charge for seniors's residents professionals: at M-1 (on 3 consecutive days) then monthly on 3 consecutive days until M6, by the housekeeper according to:

- Average meal duration
- Hospitality load: Number of interventions by the professional per resident. The average number of interventions over the 3 days will be taken into account.

**Significant events on food intake** (medical, such as an acute episode; environmental, such as a death in the family,...), which may constitute a bias for the analysis of the results, will be traced throughout the study.

Also, a follow-up of the advance medical prescriptions (AMP), oral nutritional supplements, laxatives will be carried out during the whole study.

In addition, any hospitalization, its duration and reason will be traced during the study.

This information, traced by the professionals of the service (patient file / Medical Object) will be recovered by the clinical research IDE.

# 3. STUDY DESIGN

### 3.1 GENERAL STUDY METHODOLOGY

The study has the following characteristics:

- Nursing project
- Pilot study
- Monocentric
- Prospective
- Randomized in 2 parallel arms
  - Arms without "finger-food"
  - Arms with "finger-food"
- Open

### 3.2 STUDY DIAGRAM

# 3.3 RANDOMIZATION

The randomization will be done via the Clinsight software by connecting to the website: https://nantes-lrsy.hugo-online.fr/CSOnline/.

The connection will be done thanks to a login, a password and a study number, delivered by a data-manager of the Research Promotion Department of the CHD of La Roche/Yon.

The following information must be filled in:

- First initial of the name
- First initial of the first name
- Date of birth
- Compliance with inclusion and non-inclusion criteria (yes/no)
- Collection of non-objection (yes/no).

The inclusion number will be assigned automatically during randomization. An e-mail confirmation will be sent to the person who performed the randomization and to all the persons concerned.

The randomization list will be carried out by a statistician from the Research Promotion Department of the CHD of La Roche/Yon.

A guide to the randomization procedure will be available online under Clinsight.

Randomization will be stratified by center (seniors's residents) and performed in a 1:1 ratio.

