# 4. STUDY POPULATION

# 4.1 DESCRIPTION OF THE POPULATION

All the residents of the CHD Vendée seniors's residents who meet the inclusion criteria will be able to be included in the "FIFO" trial:

- La Roche-sur-Yon : Le Marais, La Plaine
- Luçon : La Roseraie, L'Olivier
- Montaigu : Augereau, Le soleil de la Maine

Of the 269 residents institutionalized in these facilities, we estimate that about 60 subjects meet all the criteria.

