### STEP 1 : M-1 - M0

This step includes resident selection, resident unopposed, and evaluation before randomization.

• Inclusion of residents

Once the regulatory authorizations have been obtained (CPP, CNIL), the residents of the CHD Vendée's seniors's residents will be selected from all the residents meeting the inclusion and non-inclusion criteria. Then each resident and/or family/guardian will be informed by the principal investigator of each seniors's residents and a note of information and non-objection will be given to them (Appendix 2).

Initial assessment

The project will evaluate with the residents involved in the project:

**Nutritional indicators:** Nutritional intake (qualitative measurement of ingesta), weight, BMI, biological indicators, MNA screening score

Associated comorbidities: Number of wounds and pressure sores, number of falls

Autonomy: Autonomy of feeding and physical or psychological autonomy

Behavior around the meal

Resident satisfaction / enjoyment of food

Hospitality/care workload of seniors's residents professionals

Significant events on dietary intake, MAP, NOD, laxatives and any hospitalization will be tracked during this period.

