### 6.2.2 Statistical justification of the number of inclusions

To our knowledge, no clinical study has been carried out on the impact of "finger-food" in seniors's residents. Therefore, we have no data available that would allow us to make working hypotheses on its impact on the nutritional status of patients.

The purpose of this pilot study is therefore to collect preliminary data on the nutritional evolution of these patients.

No statistical calculations were performed. All residents of the 6 participating seniors's residents who met the inclusion criteria were included in the study.

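### Residents are randomised one by one in small open strata, with no fixed order of entry and no rule holding back the arms, which leaves an avoidable route to selection bias

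*Combined protocol and SAP*

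**What the plan says.** Section 3.1 describes an open trial, "Randomized in 2 parallel arms". Section 4.1 gives the expected size: "Of the 269 residents institutionalized in these facilities, we estimate that about 60 subjects meet all the criteria". Section 6.2.2 gives the number of homes and the inclusion rule: "All residents of the 6 participating seniors's residents who met the inclusion criteria were included in the study".

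On allocation, section 3.3 says that "The randomization list will be carried out by a statistician from the Research Promotion Department of the CHD of La Roche/Yon" and that "Randomization will be stratified by center (seniors's residents) and performed in a 1:1 ratio". Entry is per resident: the user types initials, date of birth and confirmation of criteria and non-opposition, and "The inclusion number will be assigned automatically during randomization". Then "An e-mail confirmation will be sent to the person who performed the randomization and to all the persons concerned".

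On timing, Step 1 of section 5.1 states: "This step includes resident selection, resident unopposed, and evaluation before randomization". The Summary gives a recruitment period of 1 month, and Step 2 starts the study meals at M0.

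The documents do not state the restriction method, the order of entry within a home, who performs the randomisation, what the e-mail contains, or any measure against prediction of the next arm.

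**The concern.** A central web system hides the list. It does not hide the running count of arms already assigned if those arms become known. Where a small stratum is kept in balance, that count tells the user which arm is more likely next. The candidates have lived in the home for at least 3 months (section 4.2), so their carers know them. If several assessed residents are waiting, the user may be able to pick the one who meets the guessed arm.

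Two kinds of error could follow:

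- **Steering on prognosis.** If residents expected to do better whatever they are fed go to finger-food, the arms differ in intake change for reasons unrelated to the meals. Subtracting baseline intake does not remove this, because the choice is made on expected change. The unadjusted Wilcoxon test of section 6.2.1 would count the difference as effect.
- **Steering on likely response.** Section 1.1 reports that in an earlier hospital evaluation finger-food seemed to work only in patients with the fewest associated pathologies who could still eat. Placing such residents in the finger-food arm could inflate a real effect. It would not create an effect where nobody benefits.

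**Working it through.** The documents give no predictability figure and no power calculation, so there is nothing to reproduce.

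**Inputs from the documents.** About 60 residents (4.1), 6 homes (6.2.2), 1:1 within home (3.3), significance level 5% (6.2.3), Wilcoxon Mann-Whitney test on change (6.2.1). Residents per home: 60/6 = 10. This is an average; the split by home is not given.

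**Assumptions.** Block size (shown as a range), arms known as assigned, a two-sided test, and a prognosis-outcome correlation r of 0.3 to 0.5.

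**Step 1: how often the next arm can be guessed.** The guesser names the arm that is behind in that home and guesses at random when the arms are level. For a complete block of 2m, the expected number of correct guesses is m + 2^(2m-1)/C(2m,m) - 1/2. The share of assignments known with certainty, if the block size is known, is 1/(m+1).

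| Block | Correct guesses | Share correct | Share certain |
|---|---|---|---|
| 2 | 1 + 2/2 - 0.5 = 1.5 | 75.0% | 50% |
| 4 | 2 + 8/6 - 0.5 = 2.83 | 70.8% | 33% |
| 6 | 3 + 32/20 - 0.5 = 4.1 | 68.3% | 25% |
| 10 | 5 + 512/252 - 0.5 = 6.53 | 65.3% | 17% |

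With 10 residents the last block of 4 or 6 is incomplete:

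- Blocks of 4: (2 x 2.833 + 0.5 + 2/3)/10 = 68.3%.
- Blocks of 6: (4.1 + 0.5 + 0.6 + 0.6 + 0.7)/10 = 65.0%.
- Unrestricted allocation: 50%.

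**Step 2: what full steering would do under no effect.** Simulated trials had 6 homes of 10. The best-prognosis remaining resident was entered when finger-food was guessed, and the worst when control was guessed. Two rules were tried when the arms were level: enter a random resident (3000 trials) or the middle one (4000 trials). The outcome depended on prognosis (correlation r) plus noise, with no treatment effect.

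| Block | Imbalance in prognosis, SD (random / middle) | Rejection, random rule, r = 0.3 / 0.5 | Rejection, middle rule, r = 0.3 / 0.5 |
|---|---|---|---|
| 2 | 0.80 / 0.94 | 13.4% / 31.0% | 18.1% / 41.9% |
| 4 | 0.50 / 0.60 | 8.2% / 14.6% | 9.7% / 18.8% |
| 6 | 0.31 / 0.36 | 6.3% / 8.4% | 6.8% / 10.3% |
| Random 4 or 6 | 0.37 / 0.43 | 6.3% / 10.6% | 8.0% / 12.8% |
| One block of 10 | 0.01 / about 0 | 4.4% / 5.1% | about 4% |
| Unrestricted | 0.00 / not run | 4.8% / 5.2% | not run |

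A further set of runs gave up to about 20% for blocks of 4.

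**Step 3: partial steering.** If a third of homes steer, rejection is about 5 to 7% with blocks of 4 or 6. Half steering with blocks of 4 gives an imbalance of about 0.29 SD and 6 to 8% rejection.

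**Step 4: entry order fixed in advance.** With blocks of 4 the arm is still guessed 68.3% of the time, but the guess cannot be used. The imbalance is -0.006 SD and rejection is 4.7 to 5.2%.

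**Step 5: steering on response.** Suppose the benefit rises by g per SD of the trait steered on, and arms are of equal size with trait difference D. The finger-food arm then sits D/2 above the average resident, so the estimated effect is too large by g x D/2. For blocks of 4 under the random rule this is g x 0.50/2 = 0.25g. The value of g is unknown, and the error is zero if nobody benefits.

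**The case against.** A reader might infer more than the documents say, in four ways:

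- **That staff see every arm by e-mail.** Section 3.3 mentions a confirmation and does not say that it names the arm. Disclosure is plausible in an open trial where catering must prepare named trays, but it is an inference.
- **That home staff choose the order.** The protocol does not say who randomises. It could be the research unit. If each resident is randomised on finishing the 3-day assessment, the calendar largely sets the order. Section 3.3 also refers to an online guide to the procedure, which is not among the documents and may settle this. The absence of a fixed order is silence, not a stated procedure.
- **That the list uses small blocks.** No restriction is stated, and leaving the block size out of a protocol can be deliberate good practice. One block per home would be natural for a closed cohort and gives almost no harm in the simulation.
- **That section 1.1 shows a route to false positives.** It describes who responds to finger-food, not who fares better in either arm. It supports the inflation in Step 5, not the rejection rates in Step 2. Those need staff to foresee 6-month change independently of arm, and no section supports a correlation of 0.3 to 0.5.

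Existing protections count too. The list is made by a statistician and served centrally. Assessment precedes randomisation. All eligible residents are to be included, so only the order can be steered, not who enters. The motive is weakened because management intends to continue finger-food (1.1) and a resident who leaves may keep it (5.3.2). The study is a pilot.

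All of this stands as a limit on size and certainty. It does not close the gap: nothing in the plan prevents arms from being known before a home's last entry, or the order from being chosen. Unrestricted allocation would avoid the guess, but would leave the stated stratification without effect. Pilot status does not dispose of the point either, since sections 6.2.1 and 6.2.3 plan between-arm tests at 5%.

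**Conclusion.** The point holds as a conditional weakness with a cheap remedy. It is not a finding that the allocation is compromised. The documents establish an open trial, individual entry, 1:1 allocation within about 10 residents per home, a message after each randomisation, and no rule on entry order or on holding back arms.

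The harm requires all of the following: arms known as assigned, small within-home blocks, a free choice among waiting residents, and staff who use it. If all hold in every home, with r of 0.3 to 0.5, false rejection is about 13 to 42% for blocks of 2, 8 to 20% for 4 and 6 to 10% for 6, depending on the rule at ties. The top figure is a worst case that needs blocks of 2, which nothing in the documents suggests. With one block per home or no restriction, rejection stays near 5%. With a third of homes steering and blocks of 4 or 6 it is about 5 to 7%. Inflation of a real effect by steering likely responders is a separate possibility that the documents do not allow to be sized.

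**What to change.** In section 3.3, replace one-at-a-time randomisation by one batch per home:

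1. Once non-opposition, eligibility and the M-1 assessment are complete for all of a home's residents, lock that home's list in Clinsight.
2. The statistician or data manager randomises the home in inclusion-number order or in a random order, using the same 1:1 allocation stratified by home.
3. All arms of the home are released together before M0.

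If inclusion-number order is used, the number must be issued at inclusion rather than at randomisation. If Clinsight cannot release a batch, fix the entry order before the home's first randomisation, for example as a random order set by the statistician. The block size need not appear in the protocol; the restriction method can sit in a document withheld from site staff.

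The cost is a change of wording and a system setting, or one short step by existing staff. No extra residents, visits or staff are needed, since the cohort is closed and the meals start only at M0. The small downside is shorter notice for catering before M0.

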# 4. STUDY POPULATION

# 4.1 DESCRIPTION OF THE POPULATION

All the residents of the CHD Vendée seniors's residents who meet the inclusion criteria will be able to be included in the "FIFO" trial:

- La Roche-sur-Yon : Le Marais, La Plaine
- Luçon : La Roseraie, L'Olivier
- Montaigu : Augereau, Le soleil de la Maine

Of the 269 residents institutionalized in these facilities, we estimate that about 60 subjects meet all the criteria.

# 4.2 INCLUSION CRITERIA

- Residents institutionalized in seniors's resident for 3 months at least
- Residents in disability to feed single-handedly because of cognitive and/or physical disorders
- Having at least use of a hand
- Do not opposing the participation in the study or information and not opposition of the family / close to confidence / legal guardian in case of resident in incapacity to understand (senility, insanity)

# 4.3 NON-INCLUSION CRITERIA

- Condined to bed
- Specific diets (without residue, allergen,...)
- Enteral nutrition
- Absence motricity of 2 hand

### 4.4 CONTRAINDICATION TO PARTICIPATION IN ANOTHER CLINICAL TRIAL

Residents will be asked not to participate in another clinical trial during the study period. Clinical trials involving oral supplements, anorectic medications, etc., could impact the resident's appetite and nutritional intake.

# 5. CONDUCT OF THE STUDY

### 5.1 GENERAL ORGANIZATION

From an ethical point of view, 2 approaches are to be considered.

On the one hand, the place and the look of the "other" in front of the resident who will eat with his fingers. The objective is to preserve conviviality, exchange and pleasure around meals, which play a central role in the regulation of human, emotional and social interrelations [25].

On the other hand, the place and role of the family and friends during mealtime must be thought out and anticipated. In fact, in seniors's residents, the participation of families, anxious to regain a place and a capacity to take charge, results in frequent assistance with meals and is willingly given by professionals, as "this is little connoted with a technicality as other care could be" [26].

An important communication campaign with these different actors is essential to prevent these 2 points.

#### **Communication to Families:**

The social life council, user representatives and families will be informed of the research project. A presentation of the study by the project leader is planned during a Social Life Council held regularly on each site of the CHD (La Roche Sur Yon, Luçon and Montaigu), followed by a display in the services for the families.

The global approach of the project and the expected results will be valued in order to limit the possible reticence linked to the Western culture and the education received which could slow down its implementation among some residents, especially the acceptability of eating with the fingers (embarrassment, dirtiness, bad education, synonymous with regression to the childhood stage, ...) [27]

Feedback from a long-term care unit in GIMONT [26] suggests that the resident should be seated in the same way as they are used to and that cutlery should be left available if they wish to use it. This aspect is important in order to preserve the custom of table use.

It is important to take into consideration the place and role of the family and friends in order to allow them to find a place with the resident, reducing the feeling of loneliness and maintaining the social link.

As for hand hygiene, residents will wash their hands before and after eating hand-held meals.

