	- Impacts on serniors's resident professionals					
	- Significant events on food intake					
	Inclusion criteria :					
	- Residents institutionalized in seniors's resident for 3 months					
	at least Decidents in dischility to food single handedly because of					
	
 
Residents in disability to feed single-handedly because of cognitive and/or physical disorders
 
					
	- Having at least use of a hand					
	- Do not opposing the participation in the study or information					
	and not opposition of the family / close to confidence / legal					
Criteria	guardian in case of resident in incapacity to understand					
	(senility, insanity)					
	Exclusion criteria :					
	- Confined to bed					
	
 
Specific diets (without residue, allergen,)
 
Enteral nutrition
 
					
	
 
Absence motricity of 2 hands
 
					
	Quantitative measurement of ingesta (caloric and protein intake),					
Primary endpoint	monthly between M-1 (before implementation of the "finger-food")					
	and M6.					
	Nutritional indicators:					
	Weight curve BMI					
	Biological indicators: Albumin / Pre-albumin, CRP					
	MNA Score Screening					
	Associated Comorbidities:					
	Number of wounds and pressure sores					
	Number of falls					
Secondary endpoint(s)	Autonomy					
	Autonomy : Power supply autonomy: EBS					
	Physical or psychological autonomy: GIR					
	Behavior around the meal:					
	- Assessment of eating disorders: Blandford scale					
	Resident satisfaction / enjoyment of food: VAS					
	Hospitality/care load of seniors's resident professionals					

Expected results	
 
This study will evaluate each of the defined evaluation criteria, analyze them in order to measure their impact on the following criteria: 
 
Maintain and/or improve the nutritional status of residents
 
Improvement of autonomy, behavior, quality of life
 
Reduction of associated comorbidities
 
 
 
Then to think about other projects, by formalising hypotheses, with an impact study.
 

------------------	--

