In spite of the respect of nutritional needs, today, the food offered to these patients is rarely effective because it is not very appetizing, always presented in the same way and consequently little consumed [13]. The notion of pleasure is no longer present. Also, as specified by A.RAYNAUD-SIMON7, "in institutions, the prevalence of undernutrition is linked to the importance of pathologies and dependence, but also to the quality of the food service and the time available to caregivers to help with feeding" [6].

In order to fight against this public health problem, the National Nutrition and Health Program

(PNNS) 3 (2011-2015) [14] has defined, through axis 3, actions to reduce the prevalence of undernutrition. In this respect, a certain number of nutritional strategies can be implemented, such as oral nutritional supplements, "homemade" enriched preparations, dietary advice, pleasure trays" or even "finger-food". Developed in seniors' for about ten years, the "finger-food" approach is not new. It has been implemented in order to meet the specific needs of residents, but without measuring its impact. This concept of "finger-food", also called "finger-food", has been particularly developed by Pr Charles Henri RAPIN8, in a geriatric unit in the Canton of Geneva (Switzerland) and consists in proposing dishes that can be seized with the fingers and eaten as such. Most often, these are individual bites with a high energy density in a small volume. The objective is to stimulate the appetite and the autonomy of people who need it [15].

There has been little research on this concept. A 2015 review of the practicalities of "fingerfood" confirms the "lack of hard evidence of its effectiveness in the scientific literature" [16].

The Nancy University Hospital has evaluated the impact of "finger-food" on the food intake of demented patients [17]. This evaluation showed a significant increase in protein intake, but it seems to be effective only in certain patients (those with the least associated pathologies and who have retained the ability to eat).

The hospital of Gimont (32) has questioned this concept of "finger-food" which would seem to maintain and/or give back autonomy to the residents, thanks to easy finger foods [18]. It would also tend to guarantee the residents sufficient nutritional intake (caloric and protein) to cover their needs, which are often increased due to the high prevalence of undernutrition or its risk in seniors's residents.

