# **1.2** SUMMARY OF BENEFITS, IF ANY, AND FORESEEABLE AND KNOW RISKS TO INDIVIDUALS INVOLVED IN THE STUDY

There are no foreseeable risks associated with participation in the study. Residents will be managed according to standard practice.

In contrast, this study seeks to demonstrate the predictable direct benefits to the residents participating in the study:

- Maintain or improve nutritional status
- Improved autonomy, behavior, and quality of life
- Reduction of associated comorbidities

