#### Information and training for professionals:

The seniors's residents and catering professionals will all be informed of the project by the project leader during plenary meetings organized on each site (3 plenary meetings per site). After this information, FIFO referents will be identified in each seniors's residents (1IDE, 2 AS and 2 MM per seniors's residents) and will be trained by the project leader. They will act as an interface between the care team and the professionals of the clinical research unit and will constitute a project resource in each seniors's residents.

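### Section 5.1 plans to promote finger-food's expected benefits to families who often help at meals in an open trial; a neutral message would remove an avoidable influence on the intake comparison

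*Combined protocol and SAP*

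**What the plan says.** - **Message to families.** Section 5.1 (Communication to Families) plans a presentation by the project leader at the social life council of each site, then a display in the wards. It adds that the overall approach and "the expected results will be valued in order to limit the possible reticence" about eating with the fingers, such as embarrassment or a sense of regression.
- **Expected results.** The Summary lists only favourable ones, beginning with "Maintain and/or improve the nutritional status of residents". Section 1.2 goes further: "this study seeks to demonstrate the predictable direct benefits to the residents participating in the study".
- **Evidence.** Section 1.1 cites a review reporting a "lack of hard evidence of its effectiveness in the scientific literature", and one hospital evaluation in patients with dementia in which protein intake rose but only some patients seemed to benefit. Section 6.2.2 says no data support a working hypothesis.
- **Families at meals.** According to section 5.1, family participation "results in frequent assistance with meals and is willingly given by professionals".
- **Design.** The trial is open (3.1). Residents are randomised 1:1, stratified by residence (3.3), so both arms share wards and dining rooms.
- **Menus.** Calories and protein are to be identical between each finger-food menu and its usual counterpart (5.1, Step 2).
- **Recording of help.** Section 2.2.2 counts interventions by professionals. Help from families is not listed.
- **Staff.** Ward and catering professionals "will all be informed of the project by the project leader during plenary meetings organized on each site" (5.1).

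**The concern.** In an open trial, people who know the allocation and influence the outcome should not be told which arm is expected to do better. Here the plan instructs that families be given such a message, and families are among those who sit with residents and help them eat. If they encourage finger-food residents more, or help control residents more to make up for a perceived loss, intake really changes, but not because of the format. This matters most for the primary endpoint. The pilot is meant to supply preliminary data for later hypotheses, so a distorted intake difference would carry over into the next study. Open allocation is hard to avoid with this intervention; promoting its benefits is not.

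**Working it through.** **1. Can encouragement reach the primary endpoint?** For a given texture and portion, write

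intake = amount offered × fraction eaten.

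Section 5.1 (Step 2) makes the calories and protein offered the same in both arms, so

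arm difference = amount offered × difference in fraction eaten.

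The fraction eaten depends on the format and on the prompting and help received. The before/after photographs in section 2.1.3 measure the total difference. They cannot divide it between format and help.

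**2. Would a difference in help be seen?** In part. Section 2.2.2 records meal duration and interventions by professionals each month over 3 days, and section 6.2.1 compares them between arms. Help from families would not appear in that count.

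**3. Does the message go beyond the protocol's own evidence?** The Summary and 1.2 list benefits only. Section 1.1 reports limited evidence with one partly positive evaluation, and 6.2.2 reports no usable data. A message built on the expected results is more favourable than these passages allow.

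**4. How large could the effect be?** The plan has no power calculation to reproduce, and no document gives the size of an expectation effect. The following is illustration only. Inputs: about 60 eligible residents (4.1), hence about 30 per arm at 1:1; 5% significance (6.2.3), taken as two-sided; no true effect; an assumed spurious shift of b standard deviations (SD) of the change in intake.

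P(significant) = Φ(b/√(2/30) − 1.96) + Φ(−b/√(2/30) − 1.96), with √(2/30) = 0.258.

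For b = 0.2: b/0.258 = 0.775, so Φ(−1.185) + Φ(−2.735) = 0.118 + 0.003 = 0.121.

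The last column gives 20,000 simulated Mann-Whitney tests (the planned test, 6.2.1) on normal data.

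| Assumed shift b (SD) | Normal approximation | Mann-Whitney |
|---|---|---|
| 0 | 5.0% | 4.6% |
| 0.1 | 6.7% | 6.3% |
| 0.2 | 12.1% | 11.3% |
| 0.3 | 21.3% | 19.7% |

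The table applies equally to a shift against finger-food. With an assumed true effect of 0.5 SD, the chance of significance by the normal approximation is 49%. A shift of +0.2 SD raises it to 77%. A shift of −0.2 SD leaves a net 0.3 SD and lowers it to 21%. These figures would apply to any bias of that size in any trial of 60; they show sensitivity and do not estimate what will happen here.

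**The case against.** The instruction has a legitimate purpose. Families may find eating with the fingers undignified, and that reluctance could itself bias the trial against finger-food. The message may only offset it, so the net direction is open. The English verb is also awkward; reading it as promotion rests on the purpose attached to it. The primary endpoint has real safeguards: photographs of the meal and its surroundings, one dietician reading them all, matched menus, and a count of staff interventions. All of this stands. It lowers the priority, but it does not make the message neutral or family help visible.

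A reader might also infer more than the documents support:

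- **That families bias the ratings.** Families rate nothing. For the Eating Behaviour Scale (EBS), "The completion of this scale will be done jointly by the caregiver and the housekeeper of the ward"; the Blandford scale is completed by the nurse and nursing assistant; for satisfaction, "This evaluation will be performed by the housekeeper or caregiver".
- **That staff raters are primed.** Section 5.1 says staff are informed of the project and referents trained. It does not say they are shown the expected results. An effect on these scales through this route is possible only if staff receive the same message.
- **That non-opposition is compromised.** Individual information comes from each residence's principal investigator with a written note (5.1, Step 1), and 11.3 requires it to be full and fair. Nothing dates the council presentation relative to that step.
- **That control residents will withdraw through disappointment.** No passage bears on this.

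**Conclusion.** The point holds in a limited form. Section 5.1 calls for the expected benefits to be promoted to families who frequently help at meals, in an open trial with both arms in the same residences, matched menus and no record of family help. This could change mealtime encouragement by arm and confound the intake comparison. The conclusion assumes that families know the resident's arm, which the open design makes likely, and that encouragement affects how much is eaten. Size and direction are unknown; the percentages above rest on assumed shifts and are not predictions. No claim about the staff-rated scales or about non-opposition follows from the documents. This is a low-priority improvement, worth making because it costs little.

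**What to change.** In section 5.1 (Communication to Families), delete the instruction to promote the expected results. Use one neutral message for the council presentations, the ward display and the staff briefings: it is not known whether finger-food changes intake, and both menus carry the same calories and protein. Keep the explanation that eating with the fingers is acceptable, since that meets the paragraph's stated purpose. Do not carry the benefit wording of section 1.2 into communication material.

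Do not require equal amounts of help in the two arms. Need for stimulation (EBS) and number of interventions are outcomes, and less need for help may be a real effect of the format. State only that the usual approach to mealtime help applies whatever the arm, in line with section 10, which describes care as otherwise identical to usual practice.

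The cost is rewording one paragraph, the slides and the poster. The downside is that some families may be more hesitant. The change removes the prompt but does not measure family help, so the report should still name this as a limitation.
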